3.2 Randomization After Completion of the Atropine Run-In Phase

After patients complete the Atropine Run-In Phase of the study, eligibility for randomization depends on amblyopic eye acuity, inter-ocular difference, and compliance with treatment.

Eligibility Criteria for Randomization:

- Amblyopic eye acuity of 20/40 to 20/160 with an inter-ocular difference of ≥ 2 lines, or amblyopic eye acuity of 20/32 with 3 lines of IOD.
- Compliance with weekend atropine treatment based on investigator judgment.

Children who do not meet the above criteria will end study participation.

3.3 Patients Who Skip the Atropine Run-In Phase

Some patients will enter the randomized trial phase of the study without participating in the Atropine Run-In Phase. These patients must have met the same applicable criteria for eligibility (see sections 2.2 and 3.2.) and must have had no improvement in amblyopic eye visual acuity between 2 visits at

269 least 6 weeks apart using the ATS HOTV protocol, confirmed by a re-test. These patients must have
270 been treated for at least 12 weeks with weekend or daily atropine by a study investigator.

271

272 For patients who skip the Atropine Run-In Phase, visual acuity will be tested in each eye using the
273 ATS HOTV visual acuity testing protocol using a study certified visual acuity tester. The testing (and
274 re-testing to confirm no improvement) of the amblyopic eye must be performed without cycloplegia
275 and with the patient wearing spectacles if prescribed (i.e., trial frames cannot be used). The better of
276 the two amblyopic eye visual acuities will serve as the baseline acuity for the Randomized Trial. If the
277 sound eye is atropinized, then the best-corrected (based on the most recent refraction) sound eye visual
278 acuity will be measured by placing the appropriate refractive correction before the sound eye.

279

Chapter 4: Randomized Trial Phase

4.1 Randomized Treatment Groups

Each patient will be randomly assigned to one of two groups:

- Intensified treatment group: Weekend atropine 1% and spectacles with plano lens over sound eye
- Control group: Weekend atropine with spectacle correction

For both the intensified treatment group and the control group:

- Treatment is continued until there is no further improvement in amblyopic eye acuity (improvement defined as ≥ 1 line) between two consecutive 10-week visits, confirmed by a re-test. Once there is no improvement of one or more lines, the patient's participation in the study is over and treatment is at investigator discretion.

Notes

1. The study will be providing atropine for all patients and new spectacles for those randomized to the plano lens group.
2. Children will be encouraged to wear a hat with a brim for outdoor activities. Nonprescription sunglasses, clip-ons, or flip-ups will be provided by the study.
3. Morning is the preferred time for administration of atropine. However, it is acceptable to administer the atropine at night if the parent/guardian has an overriding reason for it.
4. If an allergy to atropine develops, the patient can be switched to homatropine 5% after discussion with the Protocol Chair.
5. If a patient is noncompliant with treatment, the parents should be encouraged to persist with their efforts to treat to the best of their ability.
6. If a child is having difficulty in school because of treatment, the Protocol Chair should be contacted.
7. Prior to deviating from the treatment protocols or prescribing non-protocol treatment, the situation should be discussed with the Protocol Chair.

4.2 New Spectacles Prescription upon Randomization

Patients randomized to the plano lens group will be given new, study-paid spectacles (frames and lenses) upon randomization. The amblyopic eye lens prescription will be identical to the current correction and the sound eye lens prescription will be "plano." The cost of any spectacle changes prior to randomization is not covered by the study.

The parents of children receiving new glasses with the plano lens will be encouraged to go to the study optician within 48 hours to have the glasses made. Every effort should be made to have the child wearing his/her new glasses within 4 days.

Parents of all patients randomized to the atropine plus plano lens group will be given a postage paid box to return the child's original pair of glasses to the site after they pick up the new glasses with the plano lens from the study optician. The site will return the original pair of glasses to the child at the

323 time of the 10-week primary outcome exam to wear between that exam and the off-atropine exam two
324 weeks later.

325

326 **4.3 Randomization of Eligible Patients**

- 327 1. Once a patient is randomized, that patient will be included in the analysis regardless of whether the
328 assigned treatment is received or not. Thus, the investigator must not randomize a patient until
329 he/she is convinced that the parent/guardian will accept and comply with either of the treatment
330 regimens. Regardless of whether the patient receives the assigned treatment or not, the patient is
331 still considered enrolled in the study and every effort should be made to perform the follow-up
332 examinations according to the study protocol.
- 333 2. The Jaeb Center will construct a Master Randomization List using a permuted block design
334 stratified by site and treatment at enrollment (weekend or daily atropine), which will specify the
335 order of treatment group assignments. A patient is officially enrolled when the website
336 randomization process is completed.

337

338 **4.3.1 Delay in Randomization**

- 339 1. Visual acuity testing and the ocular motility examination must be performed no more than 7 days
340 prior to randomization. If randomization is delayed beyond 7 days, then these tests must be
341 repeated to confirm eligibility and establish the baseline measures for the study.
- 342 2. No other parts of the examination (including the refraction) need to be repeated if they were
343 performed within 6 months prior to randomization.

344

345 **4.3.2 Compliance**

346 A calendar log will be maintained by all families. These logs will be reviewed at each of the protocol
347 visits. The investigator's assessment of compliance will be recorded on the Follow-up Examination
348 Form.

349

350 **4.4 Follow-up Examinations**

351 All patients will have the following study visits / interactions after randomization:

- 352 • 5 weeks after randomization: telephone call
- 353 • 10 ± 1 weeks after randomization: primary outcome visit. Atropine discontinued. For patients
354 in the plano lens group, glasses with the correct lenses will be given back and the plano glasses
355 will be taken away.
- 356 • 12 ± 1 weeks after randomization: off-atropine outcome visit
- 357 • For patients whose amblyopic eye acuity has improved by ≥ 1 line at the 10-week primary
358 outcome visit, atropine will be restarted. For patients in the plano lens group, glasses with
359 plano lens will be reinstated. Visits will occur every 10 ± 1 weeks until no improvement of
360 one or more lines, confirmed by a re-test, at which point study participation ends and treatment
361 is at investigator discretion.

362

Test	Visit / Interaction				
	Baseline	5 wk phone call	Primary Outcome 10 ± 1 wk	Off-atropine Outcome 12 ± 1 wk	Every 10 ± 1 wks after primary outcome**
Telephone call		X			
Distance acuity each eye*	X		X	X	X
Ocular alignment	X			X	X
Titmus Fly				X	
Randot Preschool Test				X	

*Using ATS single-surround HOTV acuity testing protocol on a study certified visual acuity tester. The acuity testing at the 10-week primary outcome visit will be done by a masked examiner.

**For patients whose amblyopic eye acuity has improved by ≥ 1 line at the 10-week primary outcome visit. Visits occur every 10 ± 1 weeks after the primary outcome exam until no improvement of one or more lines.

Additional visits can be performed at the discretion of the investigator. A Follow-up Examination Form should be completed on the study website for every exam (not just the minimum required exams).

4.4.1 Telephone Call

Parents will be contacted by the coordinating center via telephone 5 weeks following randomization to answer any questions and to encourage compliance with treatment.

4.4.2 Primary Outcome Visit

The primary outcome visit will occur at 10 ± 1 weeks. Atropine will be discontinued at this visit.

Testing will include the following:

1. Visual acuity

- Measured in each eye (right eye first) by a certified masked examiner using the ATS single-surround HOTV acuity protocol on study certified visual acuity tester.
- The best-corrected acuity of the atropinized sound eye will be measured by placing the appropriate refractive correction before the sound eye (e.g., using lenses in trial frames if needed)
- Children who were randomized to receive atropine plus a plano lens will be tested using their old glasses for the primary outcome exam and any additional exams.

2. Re-testing of visual acuity in the amblyopic eye (if indicated)

- If amblyopic eye visual acuity has not improved from randomization by at least one line, then it will be re-tested.
- The results of the re-test will be used only to determine if the patient will continue study participation with the same study-mandated treatment. The first visual acuity will be used as the primary outcome visual acuity. If neither the test nor the re-test is one line better than the visual acuity at randomization, then study participation ends after the post-primary outcome examination.

4.4.3 Off-Atropine Outcome Visit

The off-atropine primary outcome visit will occur at 12 ± 1 weeks, 2 weeks after atropine has been discontinued at the primary outcome visit. For those patients continuing in study follow-up, atropine will be restarted after this visit; patients who were randomized to receive atropine plus a plano lens will reinstitute wearing the glasses with a plano lens. The original pair of glasses will be kept by the site and returned at the end of the study.

405 Testing will include the following:

406 1. Visual acuity

407 • Measured in each eye (right eye first) by a certified examiner using the ATS single-
408 surround HOTV acuity protocol on a study certified visual acuity tester. For those children
409 in the plano lens group, the old glasses without the plano lens will be used for acuity
410 testing.

411 2. Titmus fly and Randot Preschool Stereoacuity test

412 3. Ocular alignment assessed with the SPCT

413 4. Re-testing of visual acuity in the sound eye (if indicated)

- 414 • If sound eye visual acuity is reduced by one or more lines from its baseline acuity, then it
415 will be re-tested.
- 416 ➤ If the better sound eye visual acuity of the test and the re-test is decreased by one line
417 from baseline, and if amblyopic eye acuity improved by ≥ 1 line at the primary outcome
418 visit, then the patient will continue with the same study-mandated treatment.
- 419 ➤ If the better sound eye visual acuity of the test and re-test is 2 or more lines down from
420 baseline, then a cycloplegic refraction should be performed, and if a change in the
421 refraction has occurred, then the appropriate lenses should be placed in trial
422 frames/phoropter, and the acuity should be re-tested.
- 423 ▪ If the best-corrected acuity is still reduced by 2 or more lines from baseline and
424 there has been a significant change in refraction (as defined in Section 2.2 #6),
425 then a change in spectacle lens should be prescribed (the study will pay for this
426 change).
 - 427 ▪ If the best sound eye acuity at the outcome exam is decreased 2 or more lines
428 from baseline, then study-mandated treatment may end (per investigator
429 discretion), and the patient should return in 5 weeks to recheck the sound eye
430 acuity. This additional visit will occur regardless of whether there was a change
431 in sound eye refraction and/or there was an improvement in the amblyopic eye
432 at the primary outcome exam.
- 433

434 **4.4.4 Follow-Up Visits after the Primary and Off-Atropine Outcome Visits**

435 For patients in either treatment group with at least one line of improvement in amblyopic eye acuity at
436 the primary outcome examination, follow-up visits will occur every 10 ± 1 weeks after the primary
437 outcome exam until there is no improvement of one or more lines.

438

439 Testing will include the following:

440 1. Visual Acuity

- 441 • Measured in each eye (right eye first) by a certified examiner using the ATS single-
442 surround HOTV acuity protocol on a study certified visual acuity tester.
- 443 • The best-corrected acuity of the atropinized sound eye will be measured by placing the
444 appropriate refractive correction (equal to the most recent cycloplegic refraction) before the
445 sound eye (e.g., using lenses in trial frames if needed).
- 446 • Visual acuity in the amblyopic eye will be re-tested if visual acuity has not improved from
447 the last visit by at least one line.
- 448 • Visual acuity in the sound eye will be re-tested if visual acuity has decreased by one or
449 more lines from baseline, using the same protocol as the 12-week off-atropine outcome
450 examination – see section 4.4.3.
- 451

452 Study participation will end only after a follow-up visit at which amblyopic eye acuity shows no
453 improvement of one or more lines on both an initial test and on a confirmatory re-test (or at
454 investigator discretion if there is a reduction in best sound eye acuity of ≥ 2 lines from baseline). For
455 the first follow-up visit after the 12-week off-atropine outcome exam, the amblyopic eye acuity will be
456 compared to the acuity at the primary outcome visit for the purpose of determining improvement.
457

458 When study participation ends for patients in the 'plano' group, the plano lens may be replaced at
459 investigator discretion with a lens of proper correction purchased by the study.
460

Chapter 5: Miscellaneous Considerations

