528 atropine is discontinued, then the patient could be switched to homatropine 5%. The following
529 guidelines should be followed after discussion with the Protocol Chair:

- 530 • If a patient has a serious systemic adverse effect of atropine (such as seizure), an
531 atropine-like drug should not be prescribed.
- 532 • If a patient has mild effects that may be due to atropine such as facial flushing, then
533 homatropine should be substituted. Initially, one drop is given. If there is no adverse
534 effect in three days, then a second drop is given. If there is no problem in three days,
535 then weekend homatropine is started. Drops should be administered in the morning.

536 537 **5.5.4 Reverse Amblyopia**

538 Atropine could decrease the visual acuity in the sound eye, although this is almost always reversible.
539 In ATS1, results were inconclusive as to whether atropine produced a transient decrease in sound eye
540 acuity. However, the results indicated that treatment did not cause a permanent reduction in sound eye
541 acuity. After two years of follow up, there was no difference in sound eye acuity between the two
542 treatment groups.

543
544 In ATS1, a reduction in sound eye visual acuity (2 or more lines) occurred at 6 months more frequently
545 when a plano lens was prescribed in addition to atropine (7 of 43, 16%) compared with treatment with
546 atropine alone (4 of 123, 3%; P=0.01). However, after longer follow-up the sound eye of only one
547 patient treated with atropine alone and no patient treated with atropine plus the plano lens was worse
548 than baseline.

549
550 The diagnosis and management of reverse amblyopia at each of the study visits is left to the
551 investigator's judgment. At all post-randomization visits (if indicated), a protocol will be followed for
552 re-testing and evaluating the sound eye if it has reduced vision (see section 4.4.3).

553

554 **5.5.5 Development of Strabismus**

555 The study treatment could precipitate the development of a new manifest ocular deviation (e.g.,
556 esotropia). If this occurs, the parent(s) will be advised to have the patient see the investigator as soon
557 as possible. If a new deviation is confirmed on examination, the decision as to whether to continue or
558 discontinue therapy will be left to the investigator. If amblyopia treatment is to be discontinued prior
559 to the primary outcome exam, then the Protocol Chair should be called to discuss the situation. The

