6.2.3 Treatment Effect in Subgroups

The treatment effect in subgroups based on baseline factors will also be assessed in exploratory analyses. Interpretation of subgroup analyses will depend on whether the overall analysis demonstrates a significant treatment group difference. In the absence of an overall study difference, these subgroup analyses will be interpreted with caution.

669 The subgroups of interest are those based on visual acuity at the time of randomization, visual acuity at
670 the time of initial treatment, cause of amblyopia, length of prior treatment, maximum amount of prior
671 treatment (weekend vs daily), and age at randomization.

672

673 In accordance with NIH guidelines, a subgroup analysis of treatment effect according to gender, as
674 well as race/ethnicity, will be conducted. However, based on results from previous ATS studies, a
675 treatment effect by these variables is not expected.

676

677 The general approach for these exploratory analyses will be to repeat the primary analysis within each
678 subgroup.

679

680 **6.2.4 Stereoacuity**

681 Differences between treatment groups in stereoacuity measured at the 12-week off-atropine outcome
682 visit will be assessed using a comparison of the distributions with the exact Wilcoxon rank sum test.

683

684 **6.3 Primary Analysis for Safety**

685 **6.3.1 Sound Eye Acuity Data**

686 The loss of 2 or more lines in sound eye visual acuity from baseline to the 10-week masked exam will
687 be tabulated for each treatment group.

688

689 **6.3.2 Ocular Alignment**

690 Ocular alignment will be assessed at baseline and at 10 weeks after randomization. Development of a
691 new strabismus (no tropia at baseline and the presence of near and/or distance tropia at follow-up) or
692 an increase from baseline ≥ 10 PD will be tabulated by treatment group. Similarly, disappearance of a
693 heterotropia and a decrease in the angle of a preexisting strabismus by ≥ 10 PD will be tabulated.

694

695 **6.4 Sample Size**

696 We are unaware of any previous literature on the response to treatment of amblyopia still present after
697 initial treatment with weekend atropine. The sample size calculations were based on amblyopic eye
698 visual acuity data in a cohort of patients initially treated with weekend atropine from our previous
699 ATS4 and ATS8 studies.^{2,3} Patients in these studies were either randomized to weekend versus daily

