700 atropine or weekend atropine versus weekend atropine with a plano lens over the sound eye for the
701 initial treatment of amblyopia. In ATS4, patients had office visits at 5 and 17 weeks following
702 randomization. In ATS8, patients had office visits at 5, 10, and 18 weeks following randomization.
703 Based on improvement in visual acuity among patients defined as stable, we assumed a standard
704 deviation for the change from baseline to 10-week outcome in this study of 0.14 logMAR. We will use
705 a two-sided alpha of 0.05, with 90% power to detect difference if the true difference in change from
706 baseline between groups is 0.075 logMAR at 10 weeks. With these assumptions, and accounting for
707 5% loss to follow-up, we have calculated a necessary total sample size of 158 patients.

708

709 A minimum of 158 patients are expected to be enrolled with a goal to enroll an appropriate
710 representation of minorities. As the enrollment goal approaches, sites will be notified of the end date
711 for recruitment. Patients who have signed an informed consent form can be randomized up until the
712 end date, which means the minimum recruitment goal might be exceeded. The maximum number of
713 randomized patients will be 178.

714

715 **6.5 Interim Analysis and Sample Size Re-estimation**

716 We are unaware of any previous literature reporting on the response to treatment of amblyopia still
717 present after initial treatment with weekend atropine. The sample size estimates above are based on a
718 study of the initial treatment of amblyopia and may not match our definition of no improvement in the
719 current study. Although we feel we have been conservative in our estimate of variation, a sample size
720 re-estimation will be performed once 50% of the originally planned number of patients have completed
721 the trial. A pooled estimate of variance without respect to treatment group will be calculated and used
722 to re-estimate sample size using a procedure that maintains masking.⁹ An adjustment will be made to
723 the final alpha based upon this interim sample size re-estimation.
724

Chapter 7: References

725
726
727
728
729
730
731
732
733
734
735
736
737
738
739
740
741
742
743
744
745
746

1. Pediatric Eye Disease Investigator Group. A randomized trial of atropine vs patching for treatment of moderate amblyopia in children. *Arch Ophthalmol* 2002;120:268-78.

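### Ocular alignment at the visits after week 12 is in the Section 4.4 table but not in the 4.4.4 test list, and Section 6.3 stops both safety tabulations at week 10 while 6.2.2 carries efficacy to the last visit

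*Protocol*

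**What the plan says.** **Who continues.** Under Protocol 4.4 and 4.4.3, a child with at least one line of amblyopic-eye improvement at the 10-week exam has two weeks off atropine and then restarts it after the 12-week visit. In the plano arm the plano lens goes back on as well. The footnote to the 4.4 table reads "Visits occur every 10 ± 1 weeks after the primary outcome exam until no improvement of one or more lines".

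**What is measured there.** The 4.4 table marks ocular alignment at baseline, at the 12-week off-atropine visit and at each of the later 10-weekly visits. Section 4.4.4 gives its own test list for those later visits. It has one numbered item, visual acuity, with sub-points on testing each eye, on refracting the atropinized sound eye ("The best-corrected acuity of the atropinized sound eye will be measured by placing the" correction before it) and on re-tests. Alignment does not appear. In contrast, the 4.4.3 list for week 12 gives alignment by SPCT its own numbered item.

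**What is analysed.** Section 6.2.2 plans two between-group comparisons at the last study visit: the proportion gaining at least two lines, and mean logMAR acuity. Section 6.3.1 tabulates sound-eye loss of two or more lines up to the 10-week masked exam. Section 6.3.2 states "Ocular alignment will be assessed at baseline and at 10 weeks after randomization" and tabulates new strabismus and changes of at least 10 PD on that basis.

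**The concern.** Two things do not fit together.

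First, sites have two instructions for the same visit. One requires an alignment exam and the other does not list it. New strabismus is a treatment risk that the Protocol itself names (5.5.5). If a site works from 4.4.4, the measurement may not be made, and no later analysis plan can recover it.

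Second, the framework in Chapter 6 follows benefit further than harm. If the plano lens works, more plano than control children will enter the extension, so longer exposure will be concentrated in that arm. A report built on 6.2 and 6.3 as written would show last-visit acuity beside safety tables that end at week 10. A reader could take the 10-week safety result as describing the whole regimen.

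Harm can also shape the efficacy endpoint. Section 4.4.4 allows participation to end, at the investigator's discretion, when the sound eye is down two or more lines. Such an event can therefore fix which visit is a child's last for 6.2.2, yet 6.3 does not count it after week 10.

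**Working it through.** **1. The places side by side**

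| Item | 4.4 table | Test list in text | Analysis |
|---|---|---|---|
| Alignment, week 12 | scheduled | listed (4.4.3) | 6.3.2 names baseline and week 10 |
| Alignment, 10-weekly visits after week 10 | scheduled | not listed (4.4.4) | none in 6.3 |
| Sound-eye acuity, same visits | scheduled | listed (4.4.4) | none in 6.3; 6.3.1 ends at week 10 |
| Amblyopic-eye acuity, same visits | scheduled | listed (4.4.4) | two comparisons at last visit (6.2.2) |

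The omission in 4.4.4 cannot be read as house style, because 4.4.3 spells out alignment as its own item.

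**2. Timing.** The first extension visit falls at 10 + 10 = week 20 (± 1). Treatment stops at week 10 and restarts after week 12, so by week 20 a continuing child has had about 10 + 8 = 18 weeks of randomized treatment. The safety tabulations in 6.3 cover the first 10.

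**3. The plan's own sample size.** Section 6.4 gives "a two-sided alpha of 0.05, with 90% power to detect difference if the true difference in change from" "baseline between groups is 0.075 logMAR at 10 weeks", a standard "deviation for the change from baseline to 10-week outcome in this study of 0.14 logMAR", and then "5% loss to follow-up, we have calculated a necessary total sample size of 158 patients". By the normal approximation, n per arm = 2(1.960 + 1.282)²(0.14/0.075)² = 73.2, so 74. The two-sample t-test gives 74.2, so 75. Then 75/0.95 = 78.9, so 79 per arm and 158 in total. The stated figure reproduces. The point does not depend on it, but it supplies the SD and about 75 evaluable children per arm.

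**4. How many children the extension could hold.** One line is 0.1 logMAR. Treat the gain at week 10 as normal with SD 0.14, and put the plano mean 0.075 above control. The Protocol gives no control gain, so it is an assumption here, varied from 0 to 0.10. The share entering is 1 − Φ((0.1 − mean)/0.14).

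| Assumed control gain | Control entering | Plano entering |
|---|---|---|
| 0 | 1 − Φ(0.714) = 24%, about 18 of 75 | 1 − Φ(0.179) = 43%, about 32 |
| 0.05 | 1 − Φ(0.357) = 36%, about 27 | 1 − Φ(−0.179) = 57%, about 43 |
| 0.10 | 1 − Φ(0) = 50%, about 37 | 1 − Φ(−0.536) = 70%, about 53 |

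The re-test in 4.4.2 could add some children to both columns. Across the range the extension is a substantial part of each arm and, if the design effect is real, larger in the plano arm. These are entry numbers only. Children leave at week 20 unless they gain a further line, so fewer go on beyond that visit.

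**The case against.** **The safety of these children is not ignored.** Sound-eye acuity is measured at every extension visit with re-test rules (4.4.4), and 5.5.4 applies those rules at all post-randomization visits. Section 5.6 has treatment complications tabulated regularly for the DSMC, with no time limit. A reader might infer that late events would go unrecorded altogether; the Protocol does not support that. What stands is narrower: 5.6 names neither outcome and promises no by-arm result of the trial.

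**Chapter 6 is a synopsis that the detailed analysis plan will supersede.** That is true, and the plan, which is not at hand, may add later tables. But the Protocol does not leave the safety time point open. It fixes week 10 for both tabulations while taking efficacy to the last visit. The 4.4.4 omission concerns data collection, which an analysis plan cannot repair.

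**The earlier-trial figures do not show that week 10 misses the risk.** Section 5.5.4 says "In ATS1, a reduction in sound eye visual acuity (2 or more lines) occurred at 6 months more frequently" with plano (7 of 43, 16%) than with atropine alone (4 of 123, 3%). A reader might infer that only the extension reaches that exposure. Section 1.2 points the other way: in that trial plano was prescribed after 4 months of daily atropine, so by month 6 plano had probably been worn for about 2 months, or 8 to 9 weeks. Here it is worn for 10 weeks before the primary exam, after at least 12 weeks of atropine, making at least 22 weeks of atropine by week 10. The earlier regimen was also daily, not weekend. Section 5.5.4 adds that after longer follow-up no plano child's sound eye remained below baseline. This objection stands in full, and for the same reasons the 16% rate should not be applied to extension entrants to forecast losses.

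**The mismatch is small.** The table does carry an explicit mark, and the 4.4.4 list is not worded as exclusive, so it cannot be said that sites will omit the test. It can be said that they have conflicting instructions.

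**Conclusion.** The point holds in a limited form. The 4.4 table and 4.4.4 contradict each other on whether alignment is measured at the visits after week 12. Section 6.3 contains no analysis of sound-eye loss or alignment for that period, although 6.2.2 analyses efficacy there. Neither finding rests on an assumption; both can be read from the text.

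The size of the affected group does rest on assumptions: normal gains, the design SD and difference, and a control gain between 0 and 0.10 logMAR. The number of late harms cannot be estimated from this document. Nor does the Protocol set a planned length for the extension. Section 5.7 pays for up to four further exams, which would reach week 50 (10 + 4 × 10), and a reader might take that as the expected exposure, but it is a payment limit.

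The 10-week efficacy conclusion and the sample size are unaffected. What is at stake is whether the last-visit benefit is reported with a matching account of harm. That makes this a cheap improvement worth making, not a flaw in the primary design.

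**What to change.** 1. Reconcile 4.4.4 with the 4.4 table so that the alignment test already scheduled in the table appears in both.
2. In 6.3.1, add a descriptive by-arm table over all post-randomization visits through the last study visit: children with any sound-eye loss of two or more lines, and children with such loss still present at the last visit. The second count matters because 5.5.4 reports that earlier losses mostly did not persist.
3. In 6.3.2, add the same for new tropia and for an increase of at least 10 PD. While that section is open, also reconcile its 10-week alignment time point with the 4.4 table and 4.4.2, which schedule no alignment test at week 10.
4. Give the number of children and the duration of treatment as denominators, mark each exam as on or off atropine, and present the tables beside the 6.2.2 results.

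The cost is one line in 4.4.4 for a test the table already requires, plus a few tables from data already scheduled. The limitation is that the extension contains improvers only, and possibly different proportions of each arm. The tables should be labelled descriptive, with no between-arm test.
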